a In case of premature permanent IMP discontinuation, the participant should have a visit as soon as possible after the last IMP administration with the assessments normally planned for EOT visit (including a PK sample if the visit can be scheduled 6-7 days after the permanent IMP discontinuation). Afterwards, the participant should continue in the study up to the scheduled date of study completion and be followed according to the study procedures as specified in the protocol. Every effort should be made to have the participant complete the Week 30 and Week 56 visits' assessments (primary and main secondary endpoints) as the minimum.

For safety reasons, participants who do not want to continue to be followed in the study after IMP discontinuation should be assessed 6 weeks (±1 week) from the last IMP dose (at the minimum) using the procedure normally planned for the posttreatment follow-up visit (EOS). At the time corresponding to their Week 56 visit, all attempts will be made to contact the participant to inquire about safety and/or vital status.

Abbreviations: ADA: antidrug antibody, AE: adverse event, β-HCG: beta-human chorionic gonadotropin, BP: blood pressure, CV: cardiovascular, ECG: electrocardiogram, eCRF: electronic Case Report Form, EOS: end of study, EOT: end of treatment, FPG: fasting plasma glucose, FSH: follicle stimulating hormone, HbA1c: hemoglobin A1c, HR: heart rate, IMP: investigational medicinal product, IRT: interactive response technology, NIMP: noninvestigational medicinal product, PK: pharmacokinetic, R: Randomization, SAE: serious adverse event, SMPG: self-monitored plasma glucose, WOCBP: women of childbearing potential.

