4.3 JUSTIFICATION FOR DOSE

The selection of efpeglenatide 2, 4, and 6 mg once weekly doses is based on the results of early phase studies.

Efpeglenatide has shown increasing efficacy up to the highest dose tested. Both once-weekly 2 mg and 4 mg doses have shown clinically relevant efficacy in study HM-EXC-203. The achieved Hb1Ac reduction indicates that the dose-response plateau has not been reached with the 4 mg dose so most likely, higher efficacy of the 6 mg dose compared to the 4 mg dose can also be expected for glycemic control in diabetic patients. The once-weekly 6 mg dose tested in non-diabetic subjects in the Phase 2 study (HM-EXC-205) has shown higher efficacy in the decrease of body weight than the once-weekly 4 mg dose in this population.

Nausea and vomiting events appeared to be dose related and the trend over time showed an increase in incidence after the first injection with a general decrease thereafter for all tested doses. Based on the observed general decrease of GI event incidence after the first week of treatment with efpeglenatide, dose increases to achieve the higher doses of 4 and 6 mg (in the corresponding arm) will be in 2 mg step intervals every 2 weeks in order to minimize the GI adverse effects. The escalation step of 2 mg is small enough to contribute to improvement of GI tolerability at dose increase. With this dose escalation schedule, the dose of 4 mg once-weekly will be achieved 2 weeks and the maximal dose of 6 mg once-weekly will be achieved only 4 weeks after the first dose of efpeglenatide.

Please refer to the IB for more details ([1](#)).

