| AEs | 
All AEs will be coded to a "LLT", "PT", "HLT", and "HLGT" and associated "SOC" using the version of MedDRA currently in use by the Sponsor at the time of database lock.
 
Adverse event incidence tables will be presented by primary SOC (sorted by internationally agreed order), HLGT, HLT and PT (sorted in alphabetical order) for each treatment group, showing the number (n) and percentage (%) of participants who experienced an AE.
 
The primary focus of AE reporting will be on TEAEs. Pretreatment and posttreatment AEs will be described separately.
 
Adverse event incidence tables will be provided by treatment group for all types of TEAEs: all TEAEs, all treatment-emergent SAEs, all TEAEs leading to permanent treatment discontinuation, and all TEAEs leading to death.
 
Tables will be presented for the "30-week core on-treatment period" and for the "whole on-treatment period including the 26-week controlled Treatment Extension Period".
 
AE, SAE, and AEs leading to death tables will be presented for the 30-week on-study period too.
 |
| Hypoglycemia | 
The number (%) of participants with at least 1 hypoglycemic event during the on-treatment period will be assessed per type of hypoglycemic event (see Section 8.2.5) and according to time of occurrence (nocturnal [ie, 00:00 to 05:59 am], daytime [06:00 to 23:59]). Documented hypoglycemia (symptomatic or asymptomatic) will be also evaluated for the more stringent SMPG threshold of <3.0 mmol/L (<54 mg/dL).
 
Summaries will be presented overall and by type of event for each treatment group.
 
The total number of events (per participant-years) will be computed and summarized overall and by type of event for each treatment group.
 
Similar summaries will be also provided for the 30-week core on-treatment period.
 |

| Endpoint | Statistical Analysis Methods |
|---------------------------------|--|
| Vital signs and laboratory data | For quantitative safety parameters based on central laboratory/reading measurements, descriptive statistics will be used to summarize results and changes from baseline values by visit and treatment group. |

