2.1.4 Safety endpoints

The safety analysis will be based on the reported adverse events (AE), hypoglycemia and other safety information, such as clinical laboratory data, vital signs, and ECG.

Observation period

The observation period related to treatment will be divided into 3 main segments:

- The **pre-treatment** period is defined as the time from informed consent up to the time of first injection of IMP
- The whole **on-treatment** period is defined as the time from the first injection of the IMP up to 30 days (7 days for hypoglycemia) after the last injection of the IMP
 - The 30-week core on-treatment period is defined as the time from the first injection of IMP up to Visit 9 (Week 30) (or Day 210 if Visit 9 [Week 30] visit is missing) or up to 30 days (7 days for hypoglycemia) after the last injection of IMP, whichever comes earlier
- The **post-treatment** period is defined as the period from the end of the whole on-treatment period.

The **on-study observation period** is defined as the time from first injection of IMP up to either the last protocol-planned visit or the date of last available information if participants discontinue the study prematurely (ie, the date collected on e-CRF page “Completion of End of Study/Follow-up”), whichever is later.

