2.4.2.1 Extent of investigational medicinal product exposure

The extent of IMP exposure will be assessed by cumulative exposure (participants years), duration (days), and category (weeks).

Duration of IMP exposure is defined as last dose date - first dose date + 7, regardless of unplanned intermittent discontinuations (see [Section 2.5.3](#) for calculation in case of missing or incomplete data).

Duration of IMP exposure will be summarized descriptively as a quantitative variable (number, mean, SD, median, minimum, and maximum). In addition, duration of treatment exposure will also be summarized categorically by numbers and percentages for each of the following categories and cumulatively according to these categories: 1 to 2 weeks, 3 to 4 weeks, 5 to 8 weeks, 9 to 12 weeks, 13 to 18 weeks, 19 to 24 weeks, 25 to 30 weeks, 31 to 43 weeks, 44 to 56 weeks, and >56 weeks; cumulative duration of treatment by category (weeks) will also be summarized. The duration of treatment exposure in weeks will be the duration (in days)/7 rounded to the nearest integer.

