2.4.4 Analyses of safety data

The summary of safety results will be presented by treatment group on the “whole on-treatment period” as defined in [Section 2.1.4](#).

General common rules

All safety analyses will be performed on the safety population as defined in [Section 2.3.2](#), unless otherwise specified, using the following common rules:

- Safety data in participants who do not belong to the safety population (eg, treated but not randomized) will be listed separately

- The potentially clinically significant abnormality (PCSA) values are defined as abnormal values considered medically important by the Sponsor according to predefined criteria/thresholds based on literature review and defined by the Sponsor for clinical laboratory tests, vital signs, and ECG (PCSA version 3 date dated 21 May 2014 effective date 24 May 2014 [[Appendix A](#)])
 - PCSA criteria will determine which participants had at least 1 PCSA during the whole on-treatment period, taking into account all evaluations performed during the whole on-treatment period, including nonscheduled or repeated evaluations. The number of all such participants will be the numerator for the whole on-treatment period PCSA percentage.
 - The treatment-emergent PCSA denominator by group for a given parameter will be based on the number of participants assessed for that given parameter in the whole on-treatment period by treatment group on the safety population.
- The analysis of the safety variables will be descriptive, and no systematic testing is planned.

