2.4.4.1 Analyses of adverse events

Generalities

The primary focus of AE reporting will be on TEAEs.

If an AE date/time of onset (occurrence, worsening, or becoming serious) is incomplete, an imputation algorithm will be used to classify the AE as pretreatment, treatment-emergent, or posttreatment. The algorithm for imputing date/time of onset will be conservative and will classify an AE as treatment emergent unless there is definitive information to determine it is pretreatment or posttreatment. Details on classification of AEs with missing or partial onset dates are provided in [Section 2.5.3](#).

Incidence tables will present AEs by SOC, HLT, and PT, sorted in SOC internationally agreed order and HLT and PT sorted alphabetically for each treatment group, and the number (n) and percentage (%) of participants experiencing an AE. Multiple occurrences of the same event in the same participant will be counted only once in the tables within a treatment phase. The denominator for computation of percentages is the safety population within each treatment group.

Sorting within tables ensures the same presentation for the set of all AEs within the observation period. For that purpose, the table of all TEAEs presented by primary SOC and PT sorted by the internationally agreed SOC order and decreasing frequency of PTs within SOCs will define the presentation order for all other tables unless otherwise specified. In case of equal frequencies of PTs within a SOC, the alphabetic order will be applied. Sorting will be based on the incidence in the efpeglenatide 6 mg group.

The internationally agreed order of SOCs shown below was described in the Introductory Guide MedDRA Version 19.1, September 2016 International Conference on Harmonisation for SOC:

1. Infections and infestations
2. Neoplasms benign and malignant (including cysts and polyps)
3. Blood and lymphatic system disorders
4. Immune system disorders
5. Endocrine disorders
6. Metabolism and nutrition disorders
7. Psychiatric disorders
8. Nervous system disorders
9. Eye disorders
10. Ear and labyrinth disorders
11. Cardiac disorders
12. Vascular disorders
13. Respiratory, thoracic, and mediastinal disorders
14. Gastrointestinal disorders
15. Hepato-biliary disorders
16. Skin and subcutaneous tissue disorders
17. Musculoskeletal, connective tissue, and bone disorders
18. Renal and urinary disorders
19. Pregnancy, puerperium, and perinatal conditions
20. Reproductive system and breast disorders

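### SAP 2.4.4.1 gives adverse events only as crude percentages over a window closing 30 days after the last injection, so later-onset events are understated in any arm with more early stopping, and the protocol's 30-week on-study tables are dropped without being declared.

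*SAP*

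**What the plan says.** SAP 2.4.4 fixes one reporting period: "The summary of safety results will be presented by treatment group on the" whole on-treatment period. SAP 2.1.4 defines that period as "time from the first injection of the IMP up to 30 days (7 days for hypoglycemia) after the last injection of the IMP".

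SAP 2.4.4.1 then lists the adverse-event tables: an overview, all TEAEs, common TEAEs, serious TEAEs, TEAEs leading to discontinuation, AESIs and AERSMs. All are numbers and percentages of participants. "Multiple occurrences of the same event in the same participant will be counted only once in the tables within a treatment phase", and "The denominator for computation of percentages is the safety population within each treatment group". None uses time at risk.

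Exposure is measured elsewhere. In SAP 2.4.2.1, "The extent of IMP exposure will be assessed by cumulative exposure (participants years), duration (days), and category (weeks"). SAP 2.4.4.2 divides by participant-years, for hypoglycemia only.

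The protocol keeps people who stop IMP under observation: "the participant should continue in the study up to the scheduled date of study completion" (Protocol 1.3, footnote a). Adverse events are collected to the end of each participant's study (Protocol 8.3.1). Protocol 9.4.2, Table 7, promises adverse-event tables for the 30-week core on-treatment period and for the whole on-treatment period. It also promises tables of AEs, SAEs and AEs leading to death for a 30-week on-study period, which runs to Week 30 whether or not IMP was stopped.

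The SAP still defines the core on-treatment period but assigns no table to it. It defines an on-study period of its own and uses it only to classify deaths (2.1.4.2). SAP 1.5 records modifications to the protocol's statistical section as not applicable. SAP 1.6 names efficacy, PK and ADA and calls the document simplified, but mentions no change to the safety tables.

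**The concern.** A participant who stops IMP at Week 6 can contribute a treatment-emergent event for about 10 weeks. One who completes treatment can contribute for more than a year. Both count as one in the denominator. When the share of early stoppers differs between arms, the percentages compare unequal lengths of observation, and the arm with more stopping shows fewer of the events that need time to appear (for example pancreatic, retinal or cardiovascular events).

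Differential stopping is plausible here. Protocol 4.3 says "Nausea and vomiting events appeared to be dose related", and Protocol 7.1.1 makes confirmed intolerance a reason to withdraw from IMP. After termination, efficacy is only described, so safety is a main output of the report. The events missing from these tables are largely collected, because stoppers stay in the study. The protocol tables that would have shown them up to Week 30 are the ones the SAP omits.

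**Working it through.** The documents state no adverse-event rate and no stopping rate by arm, so there is no planned figure to reproduce. The hazards, stopping shares and stopping times below are assumptions.

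**1. Rare event, equal hazard in both arms**

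Inputs: hazard 0.05 per year; a share p stops at Week 6 (day 42) and leaves the window at day 42 + 30 = 72 (SAP 2.1.4); the others are observed for W weeks.

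Crude risk = (1 − p) × [1 − exp(−0.05 × 7W/365.25)] + p × [1 − exp(−0.05 × 72/365.25)]

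The stopper term is 0.0098. The non-stopper term is 0.0376 at W = 40 and 0.0523 at W = 56.

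| W | p = 5% | p = 15% | ratio, gap | p = 25% | ratio, gap |
|---|---|---|---|---|---|
| 40 | 3.62% | 3.34% | 0.92, 0.28 points | 3.07% | 0.85, 0.56 points |
| 56 | 5.01% | 4.59% | 0.92, 0.42 points | 4.16% | 0.83, 0.85 points |

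The true ratio is 1 throughout. Giving non-stoppers their own 30-day tail changes little (0.91 to 0.92, and 0.83 to 0.84).

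**2. Common event, equal hazard**

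Inputs: hazard 0.5 per year; stoppers' last dose on day 84, so the window ends on day 114; completers' last weekly dose at about day 385, so it ends at about day 415.

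- Completer risk: 1 − exp(−0.5 × 415/365.25) = 0.433. Stopper risk: 1 − exp(−0.5 × 114/365.25) = 0.144.
- 5% stopping: 0.95 × 0.433 + 0.05 × 0.144 = 41.9%.
- 25% stopping: 0.75 × 0.433 + 0.25 × 0.144 = 36.1%.
- Ratio 0.86, gap 5.8 points, with no true difference.
- Participant-years to first event or window end are 0.838 and 0.722 per participant. The rates are 0.419/0.838 = 0.50 and 0.361/0.722 = 0.50 per year, which are equal.

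**3. Common event, true hazard ratio 1.3**

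With 0.65 per year in the arm where 25% stop, the crude figures are 41.9% v 43.8%. Had that arm also had 5% stopping, it would show 50.5%. A gap of 8.6 points shrinks to 1.9.

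**4. Which 30-week table helps**

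The core on-treatment period ends at Week 30 or 30 days after the last injection, whichever is earlier, so a stopper leaves on the same day as before. With the inputs of step 2, risk to day 210 is 1 − exp(−0.5 × 210/365.25) = 0.250.

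- Core table: 0.95 × 0.250 + 0.05 × 0.144 = 24.5%, against 0.75 × 0.250 + 0.25 × 0.144 = 22.4%. A gap remains.
- On-study table: everyone is counted to day 210, giving 25.0% in both arms if the hazard continues off drug.

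**The case against.** **The effect is not uniform.** This stands. Protocol 2.3 describes nausea and vomiting as rising after the first injection and settling within about 2 to 4 weeks. Those events fall inside the window even after a single dose. Events that cause stopping are counted and have their own tables. A reader might infer that an arm with heavy gastrointestinal stopping would look safer overall. The documents do not support that, because its early signal would show.

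**Early termination is not the source.** This also stands. A reader might infer that the sponsor's decision to stop the study biases the comparison. It shortens follow-up, but under 1:1:1:1 randomization it should do so equally across arms on average. Only arm-specific stopping creates the bias.

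**Stopping at 6 mg is not shown to be higher.** The dose relation in Protocol 4.3 concerns the incidence of nausea and vomiting. Dose escalation is meant to reduce these events, and Protocol 7.1 treats permanent discontinuation as a last resort. The bias is conditional on a difference that nobody can read from these documents.

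**The size is small for rare events.** The worst case in step 1, 0.85 points, is less than one participant at the planned 100 per arm, in output that is descriptive with no systematic testing. Commoner events shift by several points.

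**Other output helps.** Exposure and discontinuation are reported by arm, deaths are listed for all screened participants, and events sent for adjudication are listed with study day and exposure. A careful reader could notice an imbalance, but listings do not give a comparison by arm.

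**A participant-year rate is not neutral.** The protocol itself specifies n (%), so that metric is no departure. For front-loaded events, an arm with early stopping concentrates its person-time in the high-risk weeks, and its overall rate rises. This is a reason to keep n (%) and to limit where the rate is added.

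**Conclusion.** The point holds in a limited form. The adverse-event tables make no allowance for unequal time at risk. If one arm has more early IMP stopping, its percentages for later-onset or continuing-risk events are understated. Under the rare-event assumptions (equal hazard of 0.05 per year, stopping at Week 6, 15% to 25% versus 5%), the crude risk ratio is about 0.83 to 0.92 and the gap is under 1 point. At 0.5 per year with 25% versus 5% stopping at day 84, the gap is about 6 points. These figures show the mechanism under constant hazards and predict nothing about this trial.

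One part depends on no assumption: the 30-week on-study and core on-treatment tables promised in Protocol 9.4.2 are absent from the SAP, and neither 1.5 nor 1.6 records it. The on-study tables matter more. A reader might infer that restoring the core tables would remove the bias, but that period closes 30 days after the last injection too. This is an inexpensive improvement worth making. It does not invalidate the safety report.

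**What to change.** - In SAP 2.4.4.1, for serious TEAEs, AESIs and AERSMs and their overview rows, add the number of participants with an event per 100 participant-years at risk beside n (%). Count time from first injection to first event or the end of the on-treatment period.
- Keep n (%) throughout. Treat any rate for all TEAEs together with caution, because early events are front-loaded.
- Restore the protocol's 30-week on-study tables for AEs, SAEs and AEs leading to death.
- Either restore the 30-week core on-treatment tables or record and justify their removal in SAP 1.6.

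The cost is programming and a few more columns and tables in a synopsis report. No new data are needed, but time at risk must be derived from the dose and event dates, since the exposure duration in SAP 2.4.2.1 (last minus first dose plus 7 days) is a different quantity.
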